5.1.1.4 Safety Analyses

Safety analyses will be based on the Safety Population.

No statistical hypotheses are prespecified for safety endpoints (e.g., incidence of AEs, including MACE and T2DM, clinical laboratory evaluations, vital signs, ECGs, biomarkers). Analyses will be primarily descriptive, with any p-values post-hoc and any comparative conclusions requiring confirmation.

Baseline assessments for applicable safety endpoints defined as follows:

Table 5-15 Safety Endpoint Baseline Definitions

Parameter	Description	Timing
Clinical laboratory evaluations, Vital signs, ECGs	Baseline assessment will be the last available value before the first dose of study drug for each parameter	Last non-missing assessment before first dose of study drug

5.1.1.4.1 Study Treatment Exposure and Compliance

Study treatment exposure and compliance will be summarized in total and by treatment group for the Safety Population as follows:

Table 5-16 Study Treatment Summaries

Parameter	Description	Timing	Methodology
Study treatment exposure (days)	(Treatment end date – treatment start date + 1). Number of days of treatment interruption will be subtracted from the study treatment exposure calculation.	Treatment Period	Continuous descriptive statistics
Study treatment compliance (%)	Summary by overall $100 \times \frac{\text{Number of tablets actually taken}}{\text{Number of tablets expected to be taken at the prescribed rate of 1 tablet per day (i.e., treatment end date – treatment start date + 1)}}$	Treatment Period	Continuous descriptive statistics
Categorical study treatment compliance (%)	Summary by overall 
 • < 80% • ≥ 80 and ≤ 100% • >100 and ≤ 120% • >120% 	Treatment Period	Categorical descriptive statistics

5.1.1.4.2 Adverse Events

The following adverse event (AE) terms are defined:

Table 5-17 AE Terms

Term	Description
Treatment-emergent	An event that initially occurs on or after the treatment start date, where: 
 • Treatment start date ≤ event start date ≤ (treatment end date + 30 or last follow up visit, whichever comes later) • An exacerbation of a chronic or intermittent pre-existing condition, including either an increase in frequency and/or intensity of the condition on or after the date of the first dose of study drug
Subsequent	Any event reported that occurs or worsens after last intake of study drug + 30 days.

AEs-reported as occurring after the Screening Visit, will be coded using MedDRA version 22.1 or newer. Unique subjects reporting AEs in the following AE categories will be summarized by treatment group and in total (Part 1 and Part 2) for the Safety Population as follows:

Table 5-18 AE Summaries

Parameter	Description	Timing	Methodology
Overall summary	Overall summary only for the following categories: 
 • TEAEs 
 ○ Grade 2 or above ○ Grade 3 or above • Treatment-related TEAEs 
 ○ Grade 2 or above ○ Grade 3 or above • TESAEs • Treatment-related TESAEs • TEAEs leading to study drug discontinuation • Deaths 	From treatment start date until 30 days after treatment end date or last follow up visit, whichever comes later	Categorical descriptive statistics
TEAEs	Overall summary and by SOC and PT	From treatment start date until 30 days after treatment end date or last follow up visit, whichever comes later	Categorical descriptive statistics
TEAEs by severity	Overall summary and by SOC, PT, and severity 
 • Subjects categorized overall and within each SOC and PT for the most intense occurrence • If more than one adverse event with the same preferred term was reported, then the adverse event with the greatest severity will be used. 	From treatment start date until 30 days after treatment end date or last follow up visit, whichever comes later	Categorical descriptive statistics
Treatment-related TEAEs	Overall summary and by SOC and PT	From treatment start date until 30 days after treatment end date or last follow up visit, whichever comes later	Categorical descriptive statistics
Treatment-related TEAEs by severity	Overall summary and by SOC, PT, and severity 
 • Subjects categorized overall and within each SOC and PT for the most intense occurrence 
If more than one adverse event with the same preferred term was reported, then the adverse event with the greatest severity will be used.
	From treatment start date until 30 days after treatment end date or last follow up visit, whichever comes later	Categorical descriptive statistics
TESAEs	Overall summary and by SOC and PT	From treatment start date until 30 days after treatment end date or last follow up visit, whichever comes later	Categorical descriptive statistics

Parameter	Description	Timing	Methodology
Treatment-related TESAEs	Overall summary and by SOC and PT	From treatment start date until 30 days after treatment end date or last follow up visit, whichever comes later	Categorical descriptive statistics
TEAEs leading to study drug discontinuation	Overall summary and by PT	From treatment start date until 30 days after treatment end date or last follow up visit, whichever comes later	Categorical descriptive statistics
MACE and new onset of T2DM	Overall summary and by SOC and PT 
 Includes PTs, high level terms (HLTs), and/or standardized MedDRA queries (SMQs) defined in Section 6.6.1.3 	From treatment start date until 30 days after treatment end date or last follow up visit, whichever comes later	Categorical descriptive statistics
TEAEs by subgroups of age, sex, race, and ethnicity	Overall summary and by SOC and PT	From treatment start date until 30 days after treatment end date or last follow up visit, whichever comes later	Categorical descriptive statistics

SOCs will be sorted alphabetically; PTs will be sorted in descending frequency.

All AEs (including non-treatment-emergent events) recorded on the eCRF will be listed for individual subjects showing both verbatim and preferred terms.

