Safety	
No statistical hypotheses are pre-specified for safety endpoints. Analyses will be primarily descriptive, with any p-values post-hoc and any comparative conclusions requiring confirmation.
 
Any event reported on the electronic case report form (eCRF) that occurs or worsens on or after the initiation of study drug and through 30 days after the last intake of study drug is defined as treatment-emergent. Any event reported on the eCRF that occurs or worsens after last intake of study drug + 30 days is defined as subsequent. AEs will be categorized by the Medical Dictionary for Regulatory Activities (MedDRA) preferred term and system-organ classification. The occurrence of treatment-emergent adverse events (TEAEs) will be summarized by treatment group for the safety analysis set using MedDRA preferred terms, system organ classifications, and severity. All AEs (including nontreatment-emergent events) recorded on the eCRF will be listed for individual subjects showing both verbatim and preferred terms. The number of subjects with at least one TEAE, at least one severe TEAE, at least one serious TEAE, at least one TEAE judged by the investigator to be related to study drug, and with a TEAE leading to death will be summarized by treatment group. Summaries of TEAEs will also be presented by subgroups of age, sex, race, and ethnicity.
 
Descriptive summaries of clinical laboratory results will be presented by study visit. Laboratory abnormalities will be graded according to National Cancer Institute Common Terminology Criteria for Adverse Events (NCI CTCAE) version 4.03. The number and percentage of subjects experiencing treatment-emergent graded toxicities will be summarized by treatment group and severity grade. Change from baseline in laboratory tests will be summarized for each treatment group.
 
Any abnormal findings in the physical examination or vital signs that are considered clinically significant in the opinion of the investigator will be recorded as AEs or be captured as medical history, if already present at Screening. Descriptive summaries of vital signs will be presented by study visit. Descriptive summaries of quantitative changes in vital signs will be presented by treatment group and study visit. Electrocardiogram results will be reviewed for clinically notable abnormalities according to predefined criteria. Subjects exhibiting Grade 3 or 4 PR or QT interval corrected for heart rate (QTc) interval will be summarized. Abnormalities in Fridericia's corrected QT interval (QTcF) interval, Bazett's corrected QT interval (QTcB) interval, QRS, PR, and heart rate (HR) will be summarized.

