## **11. STUDY ASSESSMENTS**

### **11.1. Demographic and Other Pretreatment Assessments: Part 1 and/or Part 2**

After written informed consent is obtained, demographic data and a complete medical and medication history will be collected at the Screening visit. A complete physical examination, including measurements of height and body weight will be performed. Medical history will be updated until the first dose of study drug. All AEs will be recorded from the time of informed consent and throughout the study, regardless of apparent causality from use of the study drug. Medications taken before the first dose of study drug will be recorded as prior medications.

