###### 11.3.1.1.2. Treatment-Emergent Adverse Events

An event will be considered a TEAE if:

- The event began on or after the date of the first dose of study drug; or
- An exacerbation of a chronic or intermittent pre-existing condition, including either an increase in frequency and/or intensity of the condition on or after the date of the first dose of study drug

An AE that occurs more than 30 days after the last dose of study drug will not be counted as a TEAE.

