4.1 Study Design Summary

4.1.1 Overall Design

This is a Phase 3, multicenter, randomized, double-blind, placebo-controlled study of CVC for the treatment of Stage 2 or 3 liver fibrosis in adult subjects with NASH. The study will be conducted in 2 parts: Part 1 (histopathological surrogate endpoint) and Part 2 (clinical outcomes).

In Part 1, approximately 1200 subjects will be randomized 2:1 to receive CVC or placebo to assess the effect of CVC on the histopathological surrogate endpoint at Month 12. Subjects continuing beyond Month 12 will remain in the same treatment arm throughout the end of the study.

Part 2 of the study will focus on assessing the effect of CVC on clinical outcomes and will include approximately 2000 subjects, of which approximately 1200 subjects will have been randomized in Part 1.

The study population will include adult subjects with a liver biopsy diagnosis of NASH and Stage 2 or 3 liver fibrosis (by NASH CRN system) as confirmed by an independent central pathologist. CVC and placebo will be administered as double-blinded study drug. Study drug (CVC or placebo) must be taken once daily with food. A Data and Safety Monitoring Board (DSMB) will be formed to review ongoing data from Part 1 and Part 2 of this study.

The study will be terminated when adjudicated events have been accrued in approximately 367 unique subjects across Part 1 and Part 2. All subjects will have an End of Study visit at that time and will return to the clinic for a Follow-up visit 30 days after the last dose of study drug.

Subjects who permanently discontinue study drug before planned end of study are encouraged to complete all subsequent study visits and participate (without treatment) in Part 2 of the study for assessment of clinical outcomes (at the discretion of the investigator, subjects who permanently discontinue study drug may be followed every 6 months unless otherwise specified by the protocol). Subjects who undergo early termination from the study will return to the clinic within 48 hours for an early discontinuation visit and will return to the clinic for a Follow-up visit 30 days after the last dose of study drug.

Survival data will be collected for all study subjects at the end of the study.

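### The SAP's treatment-emergent window can run past the protocol's 30-day limit, overlaps the SAP's own Subsequent category, and is not declared as a change

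*SAP*

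**What the plan says.** The protocol states one limit in two places. Section 11.3.1.1.2 gives two routes to a TEAE, new onset and exacerbation, and then limits both: "An AE that occurs more than 30 days after the last dose of study drug will not be counted as a TEAE". The synopsis (safety analysis) defines an event starting or worsening from first dose "through 30 days after the last intake of study drug is defined as treatment-emergent", and continues: "Any event reported on the eCRF that occurs or worsens after last intake of study drug + 30 days is defined as subsequent".

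SAP Table 5-17 sets a different upper bound: "treatment end date + 30 or last follow up visit, whichever comes later". Its second bullet, on exacerbation of a pre-existing condition, has a start date and no end date. The next row of the same table defines *Subsequent* as "Any event reported that occurs or worsens after last intake of study drug + 30 days". The timing column of Table 5-18 reads, in all ten rows, "From treatment start date until 30 days after treatment end date or last follow up visit, whichever comes later". Those rows cover the overall summary (including deaths), TEAEs, related and serious TEAEs, discontinuations, MACE and new-onset T2DM, and the demographic subgroups.

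On follow-up after stopping drug, SAP 4.1.1 says that such subjects "are encouraged to complete all subsequent study visits and participate (without treatment) in Part 2 of the study". On AE recording, Protocol 11.1 says: "All AEs will be recorded from the time of informed consent and throughout the study". Protocol 11.3.1.2 says the same, and Protocol 7.1.2 has AEs assessed at every Part 2 visit. Protocol 11.3.1.6, however, ends AE collection 30 days after the last dose.

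**The concern.** The treatment-emergent definition decides which events reach every AE summary table. In the protocol the treatment-emergent and subsequent windows meet at 30 days after the last dose and do not overlap. In the SAP they do overlap, so a programmer cannot implement both definitions as separate categories and must guess what the last follow-up visit is.

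Table 5-18 reports numbers and percentages of subjects with no adjustment for time at risk, and exposure in Table 5-16 stops at the treatment end date. Any event counted after that date plus 30 days adds to a numerator with no matching exposure. If subjects who stop drug and stay in the study differ in number between the arms, the extra events would fall unevenly. MACE and new-onset T2DM, both named safety endpoints, use this window.

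**Working it through.** No power, alpha or event-count figure is involved, so the check sets the definitions side by side.

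**1. Windows.** Let L be the date of last dose (taken as the treatment end date) and F the last follow-up visit.

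| Source | Treatment-emergent, new onset | Subsequent |
|---|---|---|
| Protocol synopsis and 11.3.1.1.2 | first dose to L + 30 | after L + 30 (synopsis) |
| SAP Table 5-17 | first dose to the later of L + 30 and F | after L + 30 |

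The SAP overlap is every onset after L + 30 and up to F. Its length is F − (L + 30) days when that is positive, and zero otherwise. Under the protocol the overlap is always zero.

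**2. Narrow reading of F.** SAP 4.1.1 schedules a Follow-up visit 30 days after the last dose. If F is that visit, F is nominally L + 30, and a visit held d days late gives an overlap of d days.

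**3. Broad reading of F.** Suppose F is the last visit attended. Assumed case, for illustration only: drug is stopped at Day 180 and the subject attends off drug to Month 96, the last visit in SAP Table 6-3. With that table's 30-day months, F = 96 × 30 = Day 2880. The protocol window closes at 180 + 30 = Day 210. The overlap is 2880 − 210 = 2670 days.

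**4. Exacerbations.** The protocol's 30-day sentence applies to both of its routes. The SAP's exacerbation bullet has no upper limit, so on its wording a worsening at any later time qualifies.

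**5. Consistency within the SAP.** Liver biochemistry (Table 5-20) uses treatment period plus 30 days. The safety End of study window (Table 6-3) ends at off-treatment Day 30. AE end-date imputation (6.4.3) targets treatment end plus 30. The AE tables are the exception.

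**6. Declared change?** SAP 5.2.2 lists PRO-C3, the ELF score and subgroup updates. The Section 8 entry for 5.1.1.4.2 lists the MedDRA version, the grade categories and related serious TEAEs. Neither mentions the window.

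**7. Can late events be in the database?** Protocol 7.1.2, 11.1 and 11.3.1.2 imply that they can, and both documents define a category for them. Protocol 11.3.1.6 implies that collection has stopped by then.

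**The case against.** The strongest reply is that the practical effect may be very small. Follow-up visit is a named visit in these documents, 30 days after the last dose (Visit 98 for subjects who reach an adjudicated outcome), and other attendances are called study visits, Early Discontinuation or End of Study. Read that way, the SAP adds only a few days. Protocol 11.3.1.6, the section on following up AEs, ends collection at 30 days; 11.3.1.5 sets the same limit for routine SAE reporting. Subjects who stop drug are kept on for assessment of clinical outcomes. The schedules of assessments that might settle the matter are not visible in the public documents. Safety analyses carry no hypotheses and are described as primarily descriptive, so no efficacy test is affected.

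Most of this stands as a limit on size. It does not remove the conflict. Even on the narrow reading, a late Follow-up visit carries the SAP window beyond a limit that the protocol states without exception, and the exacerbation bullet stays open-ended. Nor can 11.3.1.6 be relied on to keep late events out while three other protocol sections point the other way.

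A reader might also infer that single events would be counted twice. The documents do not support that: Table 5-18 has no Subsequent row, so the overlap lies in the definitions and not in any summary planned there.

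**Conclusion.** The contradiction is confirmed from the text alone and needs no assumption. The SAP's treatment-emergent rule departs from the protocol's, overlaps the SAP's own Subsequent definition, and is not declared as a change. It should be corrected before database lock.

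Its size is open. It ranges from the days by which a scheduled visit runs late to long off-drug periods in subjects followed without treatment. The upper end requires both that the last follow-up visit means the last visit attended and that AEs are still being recorded then.

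A reader might infer that the on-treatment safety comparison is materially diluted, with a definite amount of off-drug time counted as on treatment, or that it is biased in a known direction. The documents do not support either inference. They give no rate of stopping drug while staying in follow-up, no duration of that follow-up and no difference between arms. A person-time figure would also match nothing in Table 5-18, which counts subjects. The supportable statement is that off-drug events can enter these tables, in a number that cannot be estimated from the documents.

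**What to change.** - In SAP Tables 5-17 and 5-18, end the treatment-emergent window at treatment end date + 30 days and delete the extension to the last follow-up visit.
- Apply the same limit to the exacerbation bullet in Table 5-17.
- Add a descriptive Subsequent summary by treatment group, including serious events, deaths and MACE. Without it, later events would appear only in the listings, because Table 5-18 has no row to receive them.
- Reconcile Protocol 11.3.1.6 with 7.1.2, 11.1 and 11.3.1.2, so that the AE collection period for subjects followed without treatment is stated once.

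The cost is a wording change, one extra descriptive table and a protocol clarification. TEAE counts may fall slightly. No data are lost, since the SAP already lists all AEs, treatment-emergent or not.

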Subjects who progress to cirrhosis or reach an adjudicated liver-related clinical outcome will complete the study and return to the clinic for a Follow-up visit (Visit 98) 30 days after the last dose of study drug. After completion of the Follow-up visit (Visit 98), subjects will become eligible for open-label access to CVC in a separate study (Clinical Study Protocol 3152-201-002).

Part 1

At Baseline (Day 1), eligible subjects will be assigned to the treatment arms using permuted block randomization stratified by NASH CRN fibrosis stage (2 or 3) and presence or absence of documented type 2 diabetes mellitus (T2DM) (yes or no). Eligible subjects will be randomized 2:1 to one of the following 2 treatment arms:

Arm	N	Treatment
A	800	CVC 150 mg, once daily
B	400	Placebo, once daily

All subjects will undergo safety assessments at the Baseline visit and at Months 1, 3, 6, 9, and 12. The liver biopsy, used to evaluate the efficacy endpoints, must be performed within ± 2 weeks of the Month 12 visit (Visit 7).

Part 2

In Part 2, Baseline (Day 1) eligible subjects will be randomized to treatment using permuted block randomization, stratified by presence or absence of documented T2DM (yes or no). Newly enrolled subjects will be randomized 2:1 to one of the following 2 treatment arms to achieve a total of approximately 2000 randomized subjects in Part 2 (of which approximately 1200 subjects will have been randomized in Part 1):

Arm	Newly Randomized Subjects in Part 2 N	Total Subjects (Randomized in Part 1 or Part 2) N	Treatment
A	534	1334	CVC 150 mg, once daily
B	266	666	Placebo, once daily

Subjects who enter Part 2 from Part 1 of the study will have study visits every 3 months until Part 2 is completed. Study drug will be dispensed and adverse events (AEs), concomitant medications, and adherence to study drug will be reviewed at every visit (every 3 months). Safety laboratory assessments will be performed every 6 months through the end of the study.

Subjects who are randomized in Part 2 and who did not participate in Part 1 of the study will undergo safety laboratory assessments at Months 1, 6, and 12 and every 6 months thereafter through the end of the study. Beginning at Month 3, AEs, concomitant medications, and adherence will be reviewed every 3 months through the end of the study.

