5.1.1.1.3 Statistical Methodology

The methodologies defined below apply as specified to individual endpoints defined in this SAP. When indicated, 95% two-sided confidence intervals and two-sided p-values will be presented. Individual endpoint analyses may specify exceptions (additions or deletions) to these general definitions.

Table 5-2 Statistical Methodology

Methodology	Description
Categorical descriptive statistics	
 • Number and percentage of subjects in individual categories 
 ○ Subjects with ≥ 1 qualifying event counted once per individual category • N1 if denominator \neq number of subjects in the population (standard percentage denominator) 
 ○ N1 = subjects with non-missing value at corresponding visit
Continuous descriptive statistics	
 • N1, mean, standard deviation (SD), median, minimum, maximum • N1 = subjects with non-missing value
CFB descriptive statistics	
 • Continuous descriptive statistics for baseline, post-baseline, and change from baseline (CFB) values • N1 = subjects with non-missing values at both baseline and the specified post-baseline analysis visit
CFB ANCOVA	
 • Continuous descriptive statistics and standard error (SE) for baseline, post-baseline, and CFB values • Estimates derived from mixed model for CFB value controlling for factors (treatment group, fibrosis stage [2 vs 3], presence or absence of T2DM) and covariate (baseline value) 
 ○ Least squares (LS) means and SEs ○ LS mean differences, SEs, and confidence intervals (CIs) vs Placebo ○ P-values from contrast t-test comparing treatment group vs Placebo • N1 = subjects with non-missing values at both baseline and the specified post-baseline analysis visit

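### Adverse events are summarized only as crude percentages of subjects, although time at risk can differ by arm in this event-driven trial; the distortion is modest and cheap to correct

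*SAP*

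**What the plan says.** SAP 5.1.1.4.2 introduces Table 5-18 with "Unique subjects reporting AEs in the following AE categories will be summarized by treatment group and in total (Part 1 and Part 2"). Each row uses categorical descriptive statistics: treatment-emergent AEs (TEAEs), serious TEAEs, TEAEs leading to discontinuation, deaths within the overall summary, and MACE with new-onset diabetes. SAP Table 5-2 defines that method as "Number and percentage of subjects in individual categories", with "Subjects with ≥ 1 qualifying event counted once per individual category".

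The window for each row is "From treatment start date until 30 days after treatment end date or last follow up visit, whichever comes later", so its length is set by each subject's own course.

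On how long subjects are observed, SAP 4.1.1 says "Subjects who progress to cirrhosis or reach an adjudicated liver-related clinical outcome will complete the study" and "The study will be terminated when adjudicated events have been accrued in approximately 367 unique subjects across Part 1 and Part 2". SAP 5.1.2 puts the whole study at about 8 years.

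SAP Table 5-16 derives exposure in days ("Number of days of treatment interruption will be subtracted from the study treatment exposure calculation") and summarizes it by arm, but no AE table uses it as a denominator. SAP Table 5-2 defines a time-to-event method, which the plan applies to efficacy only. Neither document plans a person-time rate, Kaplan-Meier or cumulative-incidence summary for any AE. SAP 5.1.1.4 describes the status of safety: "Analyses will be primarily descriptive, with any p-values post-hoc and any comparative conclusions requiring confirmation".

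**The concern.** A crude percentage compares arms fairly when both are observed for similar lengths of time. Here the length of observation depends on the efficacy outcome. A subject with cirrhosis or an adjudicated liver outcome leaves and stops contributing AE time. If CVC prevents such outcomes, CVC subjects stay longer and more of them report at least one AE, even when the risk per year is identical.

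The opposite can also happen. Protocol 11.3.1.6 ends AE collection 30 days after the last dose, so an arm that stops drug sooner is watched for less time and can look safer. The planned tables cannot separate either mechanism from a drug effect. MACE and new-onset diabetes are named safety endpoints, and they are long-horizon outcomes for which time at risk matters.

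**Working it through.** **Inputs from SAP 5.1.2.** Placebo 80% event-free at Month 60; hazard ratio 0.62; 1334 and 666 subjects; 2-year accrual within 8 years, hence 6 to 8 years of follow-up; 20% overall dropout; 367 events.

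**Assumptions, not in the documents.** AE rates, equal in both arms; exponential times; dropout equal in both arms and reaching 20% by year 7.

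**1. Hazards.** Placebo: −ln(0.80)/5 = 0.0446 a year. CVC: 0.62 × 0.0446 = 0.0277 a year. Dropout: −ln(0.80)/7 = 0.0319 a year.

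**2. The plan's own figures.** Schoenfeld power = Φ(√(367 × 2/9) × |ln 0.62| − z). This gives 86.2% at two-sided 0.00125 (stated 85%) and 99.1% at 0.05 (stated 99%). Expected events, averaging over 6 to 8 years of follow-up: 666 × 0.2415 + 1334 × 0.1582 = 372 (stated about 367). The model reproduces the design closely.

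**3. Time on study.** Mean of (1 − e^(−sC))/s, with s = exit + dropout hazard and C the follow-up from 6 to 8 years: placebo 5.41 years, CVC 5.72 years. The gap is 0.31 years, or 5.6%.

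**4. Crude AE percentage at equal risk.** Mean of h/(h+s) × (1 − e^(−(h+s)C)), with h the AE rate:

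| AE rate per year | Placebo | CVC | Difference (points) | Ratio |
|---|---|---|---|---|
| 0.01 | 5.24% | 5.53% | 0.3 | 1.056 |
| 0.02 | 10.2% | 10.7% | 0.6 | 1.055 |
| 0.05 | 23.2% | 24.4% | 1.2 | 1.053 |
| 0.1 | 40.1% | 42.1% | 2.0 | 1.049 |
| 0.2 | 61.8% | 64.4% | 2.6 | 1.043 |
| 0.5 | 85.1% | 87.5% | 2.4 | 1.028 |

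Over follow-up patterns from 5 to 8 years, with and without dropout, the ratio runs from about 1.02 to 1.07 and the largest difference is about 3.5 points.

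**5. Scale.** The standard error of a difference near 10% is √(0.102 × 0.898/666 + 0.107 × 0.893/1334) = 1.4 points, so 0.6 points is about 0.4 standard errors. Near 25% it is √(0.25 × 0.75 × (1/666 + 1/1334)) = 2.1 points, so 1.2 points is a little over half of one.

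**6. Exits only at biopsies.** If all liver exits fall at Months 12 and 60, the exposure gap drops to 3.0%. The ratio at 0.02 a year becomes 1.029 (0.3 points), and at 0.05 a year the difference is 0.7 points.

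**7. What would reverse it.** The exit hazards differ by 0.0446 − 0.0277 = 0.017 a year, so about 1.7% a year of extra discontinuation on CVC cancels the gap and more reverses it. As illustration only, with 7 years for all, 40% stopping on CVC against 20% on placebo and AE capture ending at drug stop, the ratio at 0.02 a year is 0.93 (9.5% against 10.2%).

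**8. Does a person-year rate cure it?** With a constant hazard, yes: the rate ratio is 1.00 in every case above. With the same AE hazard in both arms at 6% in year 1 and 1% a year after (7 years, 20% dropout), the crude ratio is 1.033 and the person-year ratio 0.979. In the 40/20 illustration they are 0.957 and 1.031. A rate alone is therefore not neutral when risk changes with time.

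**The case against.** The strongest reply is that the effect is small and sits in tables labelled descriptive. That stands on size: well under one standard error at an AE rate of 2 per 100 person-years, no confirmatory test touched, and too small to hide a large harm. Exposure is also tabulated by arm, so a careful reader would see an imbalance. But mean exposure does not give time to first event for each AE type, and a descriptive label does not remove a systematic shift from the comparison.

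Other parts of the reply also stand. Laboratory, vital-sign and ECG values over time are summarized by visit and are not affected. Protocol 12.1 includes a Part 1 safety summary limited to data up to Month 12, which gives a common horizon; SAP 5.1.1.1.7, however, takes all safety data available at the Part 1 lock. Survival is collected for everyone at study end, so deaths may be less affected. Table layouts are in a separate specification not available here, although the SAP text plans no adjusted rate.

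A reader might infer more than the documents support:

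- **That stopping will make CVC look about 7% safer.** No document gives a 40/20 split. The Phase 2b study reports Year 2 withdrawals for AEs of 3.4% on continuous CVC and none on continuous placebo (Protocol 5.3.3), which indicates a possible direction and not that size. The Table 5-18 window may also extend to a later follow-up visit, and subjects who stop drug are encouraged to keep attending.
- **That the 84- and 96-month horizons bias the arms.** They differ by enrolment cohort, and both cohorts are randomized 2:1.
- **That person-year rates should replace the percentages.** Step 8 shows why not.

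**Conclusion.** The point holds as a modest one that should be corrected. Every AE category is summarized without regard to time at risk, in a trial where time at risk depends on the efficacy outcome. Under the plan's assumptions and equal AE risk, CVC would show a spurious crude ratio of about 1.03 to 1.06: roughly 0.6 points at 2 per 100 person-years and 1.2 points at 5 per 100, and about half that if liver exits come mainly at the Month 12 and 60 biopsies. This rests on the assumed AE rates, exponential times and equal dropout in the two arms. If CVC subjects stop drug earlier, the direction could reverse, by an amount the documents do not allow one to fix. A reader might conclude that the benefit-risk assessment would be overturned; at this size that does not follow.

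**What to change.** In SAP Table 5-18, for the Part 2 analysis and for Part 1 safety data beyond Month 12:

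- Add exposure-adjusted incidence rates for TEAEs, serious TEAEs, TEAEs leading to discontinuation, deaths, MACE and new-onset diabetes. Define the rate as subjects with a first event divided by person-years to first event or to the end of the TEAE window, with the rate difference and 95% CI.
- For serious TEAEs, MACE and new-onset diabetes, also add cumulative-incidence or Kaplan-Meier estimates by arm at fixed times, because the person-year rate assumes a roughly constant hazard.
- Keep the crude percentages beside them.

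State in the same place when the TEAE window ends for subjects who stop drug but continue visits, since the person-years depend on it. The cost is SAP wording and a few extra table columns; the dates are already collected. It should be settled before unblinding so that the choice of denominator cannot appear to follow the results.
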